5.1 Blood procurement for CTL and antigen-presenting cell (APC) generation

Generation of tumor-specific CTL lines requires the generation of several different components from peripheral blood mononuclear cells (PBMC). The CTL line will be derived from patient peripheral blood T cells, by stimulation with antigen-presenting cells (APCs) pulsed with pepmixes spanning the tumor-associated antigens SSX2, MAGEA4, Survivin, PRAME, and NY-ESO-1. The initial stimulation will be performed in the presence of the Th1/pro-proliferative cytokines interleukin (IL) 7, IL-12, IL-15, and IL6 and cells will be expanded in the presence of IL-2 or IL15. The APCs used to stimulate and expand the tumor-specific T cells will be dendritic cells derived from patient mononuclear cells.

For CTL generation, we will either use:

- * a mononuclear cell-apheresis collection procedure (for patients with ALCs <500) or
- * a maximum blood draw of 390 ml total, obtained in 1-3 draws over a 2 month period for CTL generation, testing for infectious viruses and HLA typing. PBMC will be separated from whole blood using ficoll gradients. T cells and monocyte-derived dendritic cells (DCs) can be prepared from fresh or cryopreserved PBMC.

To initiate tumor-specific CTL lines we will make DCs by culture of PBMC-derived monocytes with cytokines (GM-CSF, IL-4) followed by maturation with a standard DC maturation cocktail (IL-1 β , IL6, TNF α and PGE1). These mature DCs will be pulsed for 30-60 mins with a mastermix of pepmixes spanning the target antigens PRAME, SSX2, MAGEA4, NY-ESO-1 and Survivin. For dilution 1ul of each pepmix (200ng/peptide) will be added to 200ul Cell Genix/RPMI media and 50-100ul will be used to pulse the DCs ($\leq 5 \times 10^6$ DCs - 50ul; $> 5 \times 10^6$ DCs - 100ul). Subsequently the DCs will be washed once and used to stimulate PBMC-derived T cells in the presence of a T cell activating cocktail, IL7, IL15, IL12 and IL6 at a responder:stimulator ratio of at least 10:1. For initiation, DCs will be prepared from about 100mL of blood and the T cells will be derived from the monocyte-depleted PBMC fraction.

To expand the tumor-specific T cells we will use pepmix-pulsed DCs for the second and subsequent stimulations and cells will be cultured in the presence of IL-2 or IL-15. At least 100×10^6 mononuclear cells are required to generate the second batch of DCs.

At the end of the culture period, CTLs will be cryopreserved and aliquots tested for phenotype, function, specificity, identity and sterility. The frequency of tumor-specific CTLs will be determined using intracellular cytokine staining, ELISpot assay, and HLA-peptide tetramers if available. Effector memory phenotype and T cell subsets will be analyzed by flow cytometry.

Products that meet study specific release criteria, as detailed on the CofA, will be infused as per Section 5.2.

If a positive sterility testing result is reported after the product was infused, the FDA and other relevant parties would be notified as per manufacturing SOP B01.03.XX (Product Quality Assurance Program and Release and Return of Clinical GMP/GTP Products) and clinical research SOP J02.06.XX (Serious Adverse Experience and Unanticipated Problem

TACTIC

Version 1.0 6/17/2016
Version 1.1 8/12/2016

Version 1.2 11/3/2016
Version 2.0 3/20/2017

Version 3.0 6/28/2017
Version 3.1 7/24/2017

Version 3.2 11/16/2017
Version 4.0 12/03/2018

Version 4.1 7/24/2019

Reporting). Our management of such a situation is further described in our SOP F05.09.XX (Management of Culture Positive Cell Therapy Products).

We will use pepmixes produced by JPT Technologies as an antigen source. These pepmixes are overlapping peptide libraries (15 mers overlapping by 11 amino acids) spanning the entire sequence of each of the antigens of interest as per our lymphoma (TACTAL) study.

5.2 Administration and Monitoring

Patients will be evaluated in the clinic and 2 fixed doses of CTL will be administered 4 weeks apart. Patients will be monitored for clinical toxicity by the CTEP NCI Common Toxicity Criteria Scale (Version 4.X, See Section 13.3) with the exception of CRS toxicities that are related to T-cell infusions. CRS toxicities will be graded according to Appendix I. We will also analyze immunological parameters including phenotype and CTL frequencies by ELISpot and tetramer studies in patients who have HLA types for which tetramers are available. This information will be used to determine the in vivo persistence of the infused product and whether multiTAA-specific T cells will be able to recruit the patient's endogenous immune system as measured by epitope spreading. Functional analyses (antigen-specific cytotoxicity and cytokine release) will be performed by chromium release assays and ELISpot/intracellular cytokine staining, respectively. The levels of serum cytokines before and following infusion will be compared. If needed, we will compare the infused product with the patient's peripheral blood using TCR deep-sequencing. A time period of 6 weeks post the 2nd infusion will constitute the time for clinical efficacy and safety monitoring. If patients have had a partial response or have stable disease they will be eligible to receive up to 6 further doses of CTLs, each of which will consist of the same cell dose or less (if there is not enough product available for the subject's original dose) than their second infusion

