7.0 PATIENT EVALUATION

7.1 Follow up Interval

Patients shall be seen in clinic prior to the first and second infusions and evaluated (seen in clinic or contacted by a research coordinator) at 1 -2 week intervals for up to six weeks after the 2nd infusion and then at 3, 6, 9 and 12 months (post 2nd infusion). We will then continue to follow patients clinically for up to 4 additional years (total of 5 years follow-up) to evaluate long-term disease responses. If persistence of cells is noted at the 12 month visit, additional follow-up will added. Additional visits will be obtained as clinically indicated or if the patient is having more than 2 infusions.

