9.2 Data Analysis

Safety and toxicity outcomes, and laboratory evaluations will be summarized using descriptive statistics. Information on the expansion, persistence and anti-tumor effects of the adoptively transferred tumor-specific CTL will be analyzed for the immunological parameters based on multimer analysis, intracellular cytokine staining and ELISpot assays to assess the frequency of cells secreting IFN γ using the descriptive statistics such as mean, median, standard deviation at each time point. Comparison of diagnostic imaging studies from pre-infusion to 6 weeks following the second infusion will be summarized. Frequencies, proportions and their 95% confidence intervals of clinical benefit responders (adjusted to account for the two-stage nature of the design) will be summarized overall. Overall survival and progression free survival will be estimated using the Kaplan-Meier survival curve and summarized by median and 95% confidence interval.

Growth curves of immune response over time within a patient will be generated to visualize general patterns of immune response. Pairwise comparisons will compare changes of these immunological parameters from pre-infusion to each time point of post-infusion measurements using paired t-tests or Wilcoxon signed-ranks tests. Longitudinal analysis is employed to model repeatedly-measured immunologic parameters. This will allow us to model patterns of immune response per patient while allowing for varying intercepts and slopes for a patient. The normality assumption will be assessed and transformations to achieve approximate normality will be carried out if necessary.

If a patient has stable disease or a partial response as assessed by the RECIST criteria (see Section 8.4.1) after the first two infusions, they may receive up to 6 additional infusions at monthly intervals. We will collect data on the survival, immunological efficacy and anti-tumor activity of cytotoxic T-lymphocyte lines after these additional infusions so it may be compared with results obtained after the initial two infusions.

TACTIC

Version 1.0 6/17/2016
Version 1.1 8/12/2016

Version 1.2 11/3/2016
Version 2.0 3/20/2017

Version 3.0 6/28/2017
Version 3.1 7/24/2017

Version 3.2 11/16/2017
Version 4.0 12/03/2018

Version 4.1 7/24/2019

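### Persistence of the infused cells is inferred from assays that cannot show where a T cell came from; the one assay that could trace product clonotypes is optional, unscheduled and absent from the analysis section

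*Combined protocol and SAP*

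**What the plan says.** **Product.** Section 5.1: "The CTL line will be derived from patient peripheral blood T cells, by stimulation with antigen-presenting cells (APCs) pulsed with pepmixes". And: "To expand the tumor-specific T cells we will use pepmix-pulsed DCs for the second and subsequent stimulations". No gene mark or other tag is described at any step.

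**Assays and their use.** Section 5.2 lists "phenotype and CTL frequencies by ELISpot and tetramer studies in patients who have HLA types for which tetramers are available". Of these results the section then says: "This information will be used to determine the in vivo persistence of the infused product". The same sentence puts them to a second use, recruitment of endogenous immunity, which is to be judged by epitope spreading. The same paragraph adds: "If needed, we will compare the infused product with the patient's peripheral blood using TCR deep-sequencing". In both calendars in Section 7.4 the TCR row has no visit marked, and its footnote repeats the condition.

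**Analysis.** Section 9.2: "Information on the expansion, persistence and anti-tumor effects of the adoptively transferred tumor-specific CTL will be analyzed". The data named for this are multimer, ICS and ELISpot results. They are to be described at each time point, compared pairwise with the pre-infusion value and modelled longitudinally. Section 9.2 does not mention TCR sequencing or clonotypes.

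**A decision that uses the result.** Section 7.1: "If persistence of cells is noted at the 12 month visit, additional follow-up will added". It gives no definition of persistence and names no assay.

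**The concern.** ELISpot and ICS count cells that respond to an antigen, and multimers count cells that bind a given peptide-HLA complex. None of them records origin. With a gene-marked product, or a donor product that differs from the host, another assay could supply that information. Here the product is autologous and unmarked, so an infused cell and a resident cell with the same specificity look alike.

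The protocol has its own reason to expect resident cells to respond. Section 3.3 reports that lymphoma patients given cells against the same five antigens developed responses to targeted antigens and also to antigens the product was not directed at, which it interprets as antigen spreading.

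What is at stake is a mechanistic conclusion: whether the infused cells lasted, or the host response took over. This matters because Section 3.2.1 describes clinical benefit in earlier T-cell work as closely tied to persistence in vivo. Persistence at 12 months also triggers further follow-up under Section 7.1.

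**Working it through.** The plan states no figure for persistence, so there is none to reproduce. The check is whether the planned data identify the quantity that 9.2 names.

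**1. What is measured.** For the five targeted antigens, write:
- E0 = endogenous specific cells before infusion, as the assay detects them
- E0' = that same prior response at the later visit
- N = endogenous cells newly primed or expanded after infusion, as the assay detects them
- P = infused cells and their progeny still in blood
- s = the share of P that the assay detects (between 0 and 1)

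Then F(pre) = E0 and F(post) = E0' + N + sP.

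**2. What the pairwise comparison in 9.2 gives.** D = F(post) - F(pre) = (E0' - E0) + N + sP. If the prior response is stable, E0' = E0 and D = N + sP. The pre-infusion sample removes the first term only. That leaves one observed quantity and two unknown components. Taking more samples of the same kind, or modelling them longitudinally, does not separate the components.

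**3. Error if D is read as P.** D - P = N - (1 - s)P. This is positive when N exceeds (1 - s)P and negative otherwise. The documents give no value for N, s or P, so neither the sign nor the size can be determined.

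**4. Which responses are ambiguous.**

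| Response after infusion | How the plan reads it | Origin clear? |
|---|---|---|
| Against non-targeted antigens | Epitope spreading (5.2; example in 3.3) | Yes, read as recruited |
| Against the five antigens, stable since before infusion | Removed by the 9.2 comparison | Yes |
| Against the five antigens, new or increased, including new epitopes within them | Expansion or persistence of product (5.2, 9.2) | No |

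**5. Where the discriminating assay stands.** Section 7.3.4 schedules post-infusion immune samples at weeks 1, 2 and 4 after the first infusion (3), weeks 1, 2, 4 and 6 after the second (4), and months 3, 6, 9 and 12 (4): 3 + 4 + 4 = 11. Its list of uses for that blood does not include TCR sequencing, and the calendars mark sequencing at none of the 11 visits. Section 5.2 states no condition that would make it needed. The count of 11 shows the extent of the gap; it does not measure bias.

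**6. What sequencing would require.** Section 5.2 compares product with peripheral blood. Product clonotypes come from the patient's own repertoire, so finding one in post-infusion blood means little unless its frequency before infusion is known. A pre-infusion sample is therefore needed as a third element, and 5.2 does not specify one.

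**The case against.** **The TCR comparison is already in the protocol.** This is correct. A reader might infer that recruited cells would inevitably be reported as persisting product. The documents do not support that: sequencing is provided for in the same paragraph of 5.2, and 9.2 names three assays without excluding others. What remains is that the default analysis, followed as written, permits the misattribution.

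**Recruitment is measured separately.** This is partly right. Responses to non-targeted antigens are read as spreading, so it would be wrong to say that all recruited cells are counted as product. The ambiguity is confined to new or expanded endogenous cells against the five targeted antigens.

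**The error need not favour persistence.** This stands. A reader might infer that persistence can only be overstated. But infused cells that do not secrete interferon-gamma are missed by the assay readout named in 9.2, tetramers cover only some HLA types, and cells that have moved into tumor are not in the blood. An inflation factor of the form 1/(1 - e), with e an assumed endogenous share, would assume a one-way error and rest on an invented input, so none is offered.

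**Sequencing is not a full answer.** This also stands. A resident cell that shares a product clonotype and expands after infusion would count as product, and a genuine product clonotype that was common beforehand could be excluded. Sequencing every patient on, say, four samples would mean up to 4 x 22 = 88 runs. The documents do not establish that spare material exists: each 20-40 ml draw already serves several assays, draws shrink when hemoglobin is low (7.3), and product may run short (6.2). This argues against making a TCR-based definition compulsory. It does not justify keeping the present label.

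**The outcome is exploratory.** This is true, and it limits the weight of the point. In 7.1, a false positive only adds follow-up to a schedule that already runs to 5 years.

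**Conclusion.** The point holds as a mismatch between the name of an outcome and what its assays measure. For the five targeted antigens, the data specified in 9.2 identify the frequency of specific T cells in blood, not the persistence or expansion of the infused cells. The pre-infusion comparison and the separate reading of epitope spreading narrow the gap but do not close it. The only listed assay that could trace the product has no trigger, no visit and no place in the analysis.

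The size and net direction of any error are unknown and cannot be estimated from the documents. The conclusion rests on two assumptions: that the product carries no marker (none is described), and that some endogenous response to the targeted antigens can arise after infusion (plausible from 3.3, not quantified there).

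A reader might infer that the trial's efficacy conclusion is compromised. It is not. The primary endpoint is clinical benefit rate (2.1), the secondary endpoints are progression-free and overall survival (2.2), and the two-stage design and sample size (9.1.1) do not use persistence. What is affected is the mechanistic conclusion and the meaning of the trigger in 7.1. The change should be made, but the trial's main result does not depend on it.

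**What to change.** 1. In 5.2 and 9.2, report the ELISpot, ICS and multimer results as *circulating TAA-specific T-cell frequency, origin not determined*. The planned descriptive, pairwise and longitudinal analyses can stay as they are under that name.
2. Use the word persistence only for patients in whom the TCR comparison already provided for is carried out on product, pre-infusion blood and post-infusion blood. Define it as product clonotypes enriched over the pre-infusion sample, set the enrichment threshold in advance, and state that clonotypes shared with the patient's resident repertoire limit attribution. Add this analysis to 9.2 and state in 5.2 what would make the comparison needed.
3. In 7.1, say which of the two measures the 12-month persistence finding refers to.

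**Cost.** Items 1 and 3 need only amended wording. Item 2 adds no compulsory sequencing; where sequencing is done, it needs a pre-infusion sample and retained product, and their availability should be confirmed first. The downside is a less ambitious claim about persistence in patients who are not sequenced. Treatment, endpoints and sample size do not change.

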6.0 TREATMENT PLAN

This study will evaluate the clinical efficacy of T cells specific for all 5 tumor associated antigens in a fixed dose study.

6.1 Dose Levels

The patients will be treated 2 times 4 weeks apart at a fixed dose of 2×10^7 cells/m².

6.2 Dose Schedule

This protocol is designed as a phase II fixed-dose study.

Each patient will receive 2 injections at a fixed dose, 28 days apart, according to the following dose schedule: The expected volume of infusion will be 1 to 10 cc.

Dose schedule:

Day 0	2×10^7 cells/m ²
Day 28	2×10^7 cells/m ²

If patients have stable disease or a partial response by the Response Evaluation Criteria in Solid Tumors (RECIST) criteria (see 8.4.1) at their 6 week evaluation after the 2nd cell dose, they will be eligible to receive up to 6 additional doses of CTLs, At least one month

TACTIC

Version 1.0 6/17/2016
Version 1.1 8/12/2016

Version 1.2 11/3/2016
Version 2.0 3/20/2017

Version 3.0 6/28/2017
Version 3.1 7/24/2017

Version 3.2 11/16/2017
Version 4.0 12/03/2018

Version 4.1 7/24/2019

should have passed before each additional dose.. Each additional infusion will consist of the same cell number or less (if there is not enough product available for the subject's original dose) than their second infusion. Patients will not be able to receive additional doses until the initial safety profile is completed at 6 weeks following the second infusion.

6.3 Premedication

Patients may be premedicated with diphenhydramine (Benadryl) up to 1mg/kg IV (max 50mg) and acetaminophen (Tylenol) 10mg/kg po (max 650mg), though this is not mandatory.

6.4 Cell Administration:

Tumor-specific T cells will be given by intravenous injection over 1-10 minutes through either a peripheral or a central line.

6.5 Monitoring

Monitoring will be undertaken according to institutional standards for administration of blood products with the exception that the injection will be given by a physician.

6.6 Supportive Care

Patients will receive supportive care for acute or chronic toxicity, including blood components or antibiotics, and other intervention as appropriate.

6.7 Treatment Center

All treatments will be administered at the Center for Cell and Gene Therapy in Houston Methodist Hospital. Patient follow up and regular care will be at the Breast Center at Baylor Clinic or Smith Clinic.

6.8 Other Treatment

Patients should not receive other treatment for their cancer between the first and second CTL doses or for at least 6 weeks post 2nd CTL (for purposes of evaluation). If a patient receives other treatment for their cancer between the first and second CTL doses, that patient will be taken off treatment.

7.0 PATIENT EVALUATION

7.1 Follow up Interval

Patients shall be seen in clinic prior to the first and second infusions and evaluated (seen in clinic or contacted by a research coordinator) at 1 -2 week intervals for up to six weeks after the 2nd infusion and then at 3, 6, 9 and 12 months (post 2nd infusion). We will then continue to follow patients clinically for up to 4 additional years (total of 5 years follow-up) to evaluate long-term disease responses. If persistence of cells is noted at the 12 month visit, additional follow-up will added. Additional visits will be obtained as clinically indicated or if the patient is having more than 2 infusions.

7.2 History and Physical Examination

A complete history will be performed at pre-infusion, at week 2 post CTL #1, at Week 4/Day 0 (CTL infusion #2) and Weeks 1, 2, 4, 6 post CTL infusion #2, at 3, 6, 9 and 12 months, then annually for up to 4 additional years for a total of 5 years follow-up. Physical examinations will be conducted at pre-infusion for CTL #1 and on days of subsequent CTL infusions.

7.3 Other Studies

- 7.3.1 The following investigations will be obtained at pre-infusion for CTL #1 and on days of subsequent CTL infusions

CBC and differential and Complete Metabolic Panel (CMP).

- 7.3.2 Pregnancy testing is required on female patients of childbearing potential prior to CTL infusion #1. Pregnancy testing is not required prior to CTL infusion #2 for patients treated.

- 7.3.3 Diagnostic imaging (CT scans, MRI, nuclear imaging) and/or blood tests (serum cytokines) to document measurable disease and response to therapy at pre-infusion and 6 weeks following the second infusion. The time may vary by 1-2 weeks due to scheduling issues and may be done earlier if clinically indicated. The choice of imaging will depend on what studies have been most informative in following the patient's disease. If diagnostic imaging studies are performed at other times either during or after treatment on this study, that data will be collected and information gained will be used for this study.

- 7.3.4 The following investigations will be obtained pre-infusion, and at 1, 2, 4 weeks after the first infusion and then at 1, 2, 4, 6 weeks and 3, 6, 9, and 12 months following the 2nd infusion. 20-40ml of peripheral blood will be collected in preservative-free heparin anticoagulant. This blood will be used for analysis of specificity of CTL response using HLA-peptide tetramer analysis and immune function assays including ELISpot, intracellular cytokine staining and cytotoxicity assays. Serum will be batched for analysis of blood cytokine levels. These studies will be done on patients on whom the appropriate reagents are available.

- 7.3.5 If the patient has additional injections of cells after the first 2 infusions, the tests listed in 7.2.1 and 7.2.4 will also be obtained pre each infusion, and at 1, 2, 4, and 6 weeks post each infusion. Follow up will then continue at 3, 6, 9 and 12 months after the last infusion. No study specific blood tests will be done after two years (if the patients have had additional injections) but we will continue to follow patients clinically once a year for up to 4 additional years (total of 5 years follow-up) to evaluate long term disease responses.

- 7.3.6 Other Tissues: Should the patient undergo a tumor biopsy at any time while they are on study, a sample of this will be used to assess the tumor antigen expression profile.

TACTIC

Version 1.0 6/17/2016
Version 1.1 8/12/2016

Version 1.2 11/3/2016
Version 2.0 3/20/2017

Version 3.0 6/28/2017
Version 3.1 7/24/2017

Version 3.2 11/16/2017
Version 4.0 12/03/2018

Version 4.1 7/24/2019

If a patients' hemoglobin is less than 7.0g/dl at any of the evaluation times, the amount of blood drawn for the evaluation will be reduced and may be obtained over more than one venipuncture, if necessary.

All pre-study exams must be done within 72 hours of eligibility.

TACTIC

Version 1.0 6/17/2016
Version 1.1 8/12/2016

Version 1.2 11/3/2016
Version 2.0 3/20/2017

Version 3.0 6/28/2017
Version 3.1 7/24/2017

Version 3.2 11/16/2017
Version 4.0 12/03/2018

Version 4.1 7/24/2019

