7.4 Summary of Monitoring

Study Calendar: A summary of monitoring studies is provided in the following table:

Study Procedure	Treatment														Follow-up			
	Pre-infusion	Day 0	Wk 1	Wk 2	Wk 4/Day 0 [#2]	Wk 1 [#2]	Wk 2 [#2]	Wk 4 [#2]	Wk 6 [#2]	M 3	M 6	M 9	M 12	Y 2	Y 3	Y 4	Y 5	
STUDY DRUG ADMINISTRATION																		
mTAA CTL infusion		X			X													
DATA/TESTS/SPECIMENS TO BE OBTAINED																		
Blood Procurement ^a	X																	
Concomitant Medications		X																
PE	X				X													
Hx	X			X	X	X	X	X	X	X	X	X	X	X	X	X	X	
Pregnancy Test ^b	X																	
Blood Tests [Hematology, Comprehensive Metabolic Panel] ^c	X				X													
Imaging studies ^d	X								X									
Immune function studies ^e	X		X	X	X	X	X	X	X	X	X	X	X					
TCR deep-sequencing ^f																		
Tumor Biopsy ^g																		
DATA REVIEW																		
Eligibility Assessment for Procurement	X																	
Eligibility Assessment for Therapy		X																
Breast Cancer Information	X																	
AE Assessment		X ^h																
Response Assessment									X ⁱ									
Follow-up										X	X	X	X	X	X	X	X	
Follow-up Cancer																		
Follow-up Pregnancy																		
Relapse and Progression Assessment																		
Death																		

a- Blood will be collected for infectious disease testing, HLA typing, and mTAA CTL generation

TACTIC

Version 1.0 6/17/2016
Version 1.1 8/12/2016

Version 1.2 11/3/2016
Version 2.0 3/20/2017

Version 3.0 6/28/2017
Version 3.1 7/24/2017

Version 3.2 11/16/2017
Version 4.0 12/03/2018

Version 4.1 7/24/2019

- b- Pregnancy testing will be done pre-infusion in patients of childbearing potential. Either serum or urine is acceptable
- c- Hematology labs for CBC with differential WBC count; Comprehensive Metabolic Panel includes BUN, creatinine, bilirubin, SGOT, SGPT, alkaline phosphatase, sodium, potassium, chloride, carbon dioxide, albumin.
- d- Imaging studies required per section 7.3.3; imaging studies will be performed on a case by case basis to assess disease status at the discretion of the treating physician.
- e- Blood will be used for immune function assays including ELISPOT and cytotoxicity assays per section 7.2.4
- f- If required, TCR deep-sequencing will be performed to compare the infused product with the patient's peripheral blood per section 5.2

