8.0 RESPONSE CRITERIA

A 6-week period after the second infusion will constitute a course, which will be evaluated for critical toxicity, and a 6-week period after the second CTL infusion will be required for evaluation for antitumor activity.

Patients with measurable disease will be assessed by standard criteria to determine clinical response. Evaluations of tumor size will be performed pre-infusion and 6 weeks after the second injection. Additional imaging performed as part of standard clinical care will also be evaluated. All patients who receive CTL infusion and continue to be enrolled on the study will be evaluable for response. Patient long term overall and progression free survival will also be evaluated at 1 year and then annually for up to an additional 4 years (total of 5 years follow-up).

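### In the initial course no blood count or chemistry panel is scheduled in the 6 weeks after infusion 2, the period the plan uses to judge toxicity, and 10 of up to 12 research draws have no scheduled hemoglobin

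*Combined protocol and SAP*

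**What the plan says.** **Safety laboratory tests.** Section 7.3.1 covers the CBC with differential and the CMP: "The following investigations will be obtained at pre-infusion for CTL #1 and on days of subsequent CTL infusions". In the main calendar (7.4), the row that begins "Blood Tests [Hematology, Comprehensive Metabolic Panel" is marked at Pre-infusion and at Wk 4/Day 0 [#2] and nowhere else.

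**Toxicity window.** Section 8.0 states: "A 6-week period after the second infusion will constitute a course, which will be evaluated for critical toxicity". Section 6.2 adds: "Patients will not be able to receive additional doses until the initial safety profile is completed at 6 weeks following the second infusion".

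**Research blood.** Section 7.3.4 takes 20-40 mL before infusion and then "at 1, 2, 4 weeks after the first infusion and then at 1, 2, 4, 6 weeks and 3, 6, 9, and 12 months" after the second infusion. The immune-function row of the main calendar matches.

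**Hemoglobin rule.** The text closing 7.3 reduces the volume drawn under this condition: "If a patients' hemoglobin is less than 7.0g/dl at any of the evaluation times". Eligibility admits patients at Hgb 7.0 or above (4.1.4, 4.3.7), and both criteria refer to 7.3.

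**Additional infusions.** Section 7.3.5 asks for the tests of 7.2.1 and 7.2.4 before each additional infusion and at weeks 1, 2, 4 and 6 after it. The Additional Treatment calendar marks blood tests on Day 0 only.

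**The concern.** The plan names a period for judging toxicity but schedules no count, liver test or renal test in it. Three rules depend at least partly on such values: the halt after two possibly related grade 4 events (9.4), the end of treatment for related organ toxicity of grade III or higher (10.1.1), and the CRS scale, which uses organ-toxicity grades and grade 4 transaminitis (Appendix I). An asymptomatic laboratory abnormality after infusion 2 has no scheduled route into any of them.

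This also limits what can be reported. Section 9.2 promises descriptive summaries of toxicity and laboratory evaluations. If few values exist after infusion 2, a clean table cannot separate absence of toxicity from absence of measurement, and the missing values cannot be recovered later.

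The hemoglobin rule has the same weakness. It is written for every evaluation time, in a population admitted down to 7.0, but most evaluation times carry no scheduled hemoglobin.

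**Working it through.** The plan states no total of draws or tests to reproduce, so the check is a count of scheduled time points, made in both the text and the calendar.

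**1. CBC/CMP in the initial course (7.3.1; 7.4).** Pre-infusion and the day of infusion 2 (day 28) make 2. Text and calendar agree, so a damaged table is not the explanation.

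**2. Toxicity window (8.0, 6.2).** It runs for 6 weeks from day 28, that is to day 28 + 42 = day 70. CBC/CMP scheduled after the day of infusion 2 and up to day 70: 0. The day-28 sample gives one look after infusion 1.

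**3. Research draws (7.3.4; 7.4).**
- Pre-infusion: 1
- Weeks 1, 2 and 4 after infusion 1: 3 (week 4 is the day of infusion 2)
- Weeks 1, 2, 4 and 6 after infusion 2: 4
- Months 3, 6, 9 and 12: 4

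Total 1 + 3 + 4 + 4 = 12, and the calendar row also has 12 marks.

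**4. Draws with a scheduled hemoglobin.** Pre-infusion and the day of infusion 2, so 2. Draws without: 12 - 2 = 10, namely weeks 1 and 2 after infusion 1 and all 8 after infusion 2.

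**5. Volume.** Without a scheduled hemoglobin: 10 x 20 = 200 mL to 10 x 40 = 400 mL, out of 12 x 20 = 240 mL to 12 x 40 = 480 mL. After infusion 2 alone: 8 x 20 = 160 mL to 8 x 40 = 320 mL. These are maxima spread over more than a year, because 7.3.4 limits the studies to patients for whom reagents are available.

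**6. Patients affected.** Everyone who receives infusion 2. The ceiling is the 22 to be accrued (9.1.1). Since 9.3 counts as evaluable only patients given both infusions, full accrual implies at least 17, and a stop after stage 1 at least 9.

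**7. Initial course against additional infusions.** Section 7.2 has no numbered items, so 7.2.1 and 7.2.4 in 7.3.5 appear to be outdated numbers for 7.3.1 and 7.3.4. Calendar footnotes e and g support this: they cite 7.2.4 for immune assays and 7.2.6 for biopsy tissue, which now stand at 7.3.4 and 7.3.6. On that reading, the text schedules CBC/CMP at weeks 1, 2, 4 and 6 after an additional infusion, which only some patients receive, and at none of those weeks after infusion 2. The Additional Treatment calendar, with Day 0 only, contradicts 7.3.5.

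**The case against.** Text and main calendar agree, so this may be a deliberately light schedule. The protocol reports 18 lymphoma patients treated without adverse events (3.3). History is taken at weeks 1, 2, 4 and 6 after infusion 2 (7.2), adverse events are assessed throughout the monitoring period (7.4), extra visits are allowed when clinically indicated (7.1), and chemistries and hematologic parameters are to be kept on all patients (11.0). Event collection also follows SOPs that are not part of the document.

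Much of this stands, and it rules out several stronger inferences.

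- **That re-dosing proceeds without any laboratory check after infusion 2.** It does not: 7.3.1, 7.3.5 and the Additional Treatment calendar all place a CBC/CMP at or before each additional infusion.
- **That the hemoglobin rule cannot work.** It is conditional and can act on any available value, including one from routine care. What is missing is a value that the protocol schedules.
- **That nothing is measured in practice.** The documents cannot show this. They show only that nothing is scheduled.
- **That the primary analysis suffers.** The clinical benefit endpoint and the two-stage rule in 9.1.1 do not use these values.

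The remaining defense is weaker. Keeping records of chemistries does not schedule them. History may be taken by coordinator contact (7.1), and physical examination is limited to pre-infusion and infusion days (7.2), so neither detects a silent abnormality. Eighteen patients with another disease give reassurance about expected risk but do not replace measurement here.

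**Conclusion.** The point holds as a gap in scheduled measurement. In the initial course no CBC or CMP is scheduled in the 6 weeks after infusion 2, and none later for patients who are not re-dosed. Laboratory-based grading has no scheduled input in the window that the plan itself defines, and 10 of up to 12 research draws have no scheduled hemoglobin. Separately, 7.3.5 conflicts with the Additional Treatment calendar.

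This should be fixed. It bears on patient safety and on what the safety summary can show, but not on the efficacy decision. The counts assume that a patient completes every planned visit and draw; the identification of 7.2.1 and 7.2.4 with 7.3.1 and 7.3.4 is an inference from the numbering.

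**What to change.** Reconcile 7.3.1, 7.3.5, the hemoglobin rule and both calendars with the 6-week toxicity window:

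- Schedule CBC/CMP at post-infusion visits of the initial course where 7.3.4 already draws blood, as 7.3.5 does for additional infusions.
- Schedule a hemoglobin with the later research draws, so that the draw-reduction rule has a value to act on.
- Correct the section numbers in 7.3.5 and the calendar footnotes, and make 7.3.5 and the Additional Treatment calendar agree.
- State which laboratory data make up the initial safety profile in 6.2.
- In reporting, give the number of patients with a laboratory value at each time point, so that unmeasured is not read as normal.

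The exact time points, and whether any laboratory condition attaches to re-dosing, are for the sponsor to decide.

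The cost is an amendment to the text and calendars, routine tubes at existing draws (a few mL more blood), and more low-grade laboratory adverse events to record. A patient who has no research draw, or who would only have been contacted by a coordinator, might need a clinic visit.
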